6.7.2. Adverse Events Severity

For graded adverse event summaries, AEs with no grade reported will be graded as severe.

6.7.3. Missing Start and Stop Dates for Adverse Events

Missing start date and times will be handled as follows:

- AE onset date completely missing:
 - If AE is not ongoing and AE onset date missing and AE end date missing, then impute AE onset as date/time of first dose.
 - Else if AE is not ongoing and AE onset date missing and AE end date not missing and date/time of first dose \leq AE end date, then impute AE onset as date/time of first dose of study drug.
 - Else if AE is not ongoing and AE onset date missing and AE end date not missing and AE end date is BEFORE first dose of study drug, then impute AE onset as AE end date YEAR and MONTH with 01 as the day and 00:00 as time.
 - Else if AE IS ongoing and AE onset date missing, then impute AE onset as date/time of first study drug dose.
- AE onset date has year and month only:
 - If AE onset date has year and month only and they are the year and month of first dose of study drug, then impute AE onset as date/time of first dose:
 - Else if AE onset date has year and month only and date/time of first dose is not missing, then impute AE onset as AE onset year and month with 01 as the date and 00:00 as the time.
- AE onset date has year only:
 - If AE onset date has year only and it is year of first dose of study drug, then impute AE onset as date/time of first dose of study drug.
 - Else if AE onset date has year only and date of first study drug dose is not missing and year of AE onset is NOT the year of first dose of study drug, then impute AE onset as Jan. 1 of the AE onset year and 00:00 as the time.
- AE onset missing (where it was not handled by the above cases):
 - If AE onset date is missing, then impute AE onset as date/time of first study drug dose.
- AE onset has complete date but missing time:
 - If AE onset date is a date only and is same as date of first study drug dose, then impute AE onset as date/time of first study drug dose.
 - Else if AE onset date is a date only and is NOT = date of first study drug dose, then impute AE onset as AE onset date with 00:00 as the time.

Missing end date and times will be handled as follows:

- AE end date - completely missing:
 - If AE is not ongoing and both AE onset and AE end dates are missing, then impute AE end date as date/time of last study drug dose.
 - Else if AE is not ongoing and AE onset date not missing and AE end date missing AND AE onset date \leq date/time of last dose, then impute AE end date as date/time of last study drug dose.
 - Else if AE is not ongoing and AE onset date is not missing and AE end date is missing and date of last dose is not missing and AE onset is AFTER date of last dose, then impute AE end date as the last day of the month of AE onset date, with 23:59 as time.
- AE end date = year and month only:
 - If AE is NOT ongoing and AE end date consists of year and month only, then impute AE end date as the last day of the month of AE end date month and year, with 23:59 as time.
- AE end date = year only:
 - If AE is NOT ongoing and AE end date consists of a year only, and year = year of AE onset and AE onset date \leq date of last study drug dose, then impute AE end date as the date of last study drug dose.
 - Else if AE is NOT ongoing and AE end date consists of a year only, and year = year of AE onset and AE onset date $>$ date of last study drug dose, then impute AE end date as the year and month of AE onset, with the last day of the month as the day, and 23:59 as the time.
- AE end date = complete date but no time:
 - If AE is NOT ongoing and AE end date consists of a complete date but no time, then impute AE end date = trim (AE end date) || "T23:59".

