#### **8.2.4 Time Period and Frequency for Event Assessment and Follow-up**

AEs will be recorded from the time the ICF is signed until the end of the follow-up period. AEs will be assessed at each study visit, and subjects should be encouraged to contact the study site

to report AEs that occur between scheduled visits. AEs that occur in the time period between informed consent and the first dose of study drug should be recorded but will not be considered TEAEs. If the AE occurs on the date of the first dose of study drug, the time of onset will be captured to determine whether the AE occurred before or after study drug administration.

After the initial AE/SAE report, the Investigator is required to proactively follow each subject at subsequent visits/contacts. All AEs/SAEs will be followed until resolution, stabilization, the event has been shown to be unrelated to study drug, or the subject is lost to follow-up (as defined in [Section 7.4](#)).

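### SAP 6.7.3 sets partial AE onset dates to first dose without checking the AE end date, so an event that ended before dosing can get an onset after its own end and be counted as treatment-emergent

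*SAP*

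**What the plan says.** SAP 6.7.3 has separate branches for different degrees of missing onset.

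- Year and month known: the test is "If AE onset date has year and month only and they are the year and month of first dose of study drug". When it is met, onset goes to the moment of first dosing.
- Year only known: the test is "If AE onset date has year only and it is year of first dose of study drug". The result is the same.
- Onset wholly missing: here the end date is consulted. If the "AE end date is BEFORE first dose of study drug, then impute AE onset as AE end date YEAR and MONTH", with day 01 and time 00:00.

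The end-date rules in the same section leave a complete end date where it is. The rule beginning "If AE is NOT ongoing and AE end date consists of a complete date but no time" only adds 23:59. A year-and-month end goes to the end of its month: "If AE is NOT ongoing and AE end date consists of year and month only, then impute AE end date as the last day". No rule requires imputed onset to be no later than end.

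Treatment-emergent AEs (TEAEs) are defined more than once. SAP 8.1 includes the date of first dose. Protocol 8.2.1 includes events during or after the first dose. SAP 6.6.2 requires a start later than the first-dose date and time, and Table 4 in SAP 6.6.4 reads the same way. Protocol 8.2.4 and SAP 6.6.2 agree that pre-dose events are not TEAEs.

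Pre-dose events are collected: "AEs will be recorded from the time the ICF is signed until the end of the follow-up period" (protocol 8.2.4). SAP 6.6.2 restricts the AE tables to TEAEs.

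**The concern.** Moving an uncertain onset to first dose is a normal conservative convention: if an event might have begun on treatment, count it. That reasoning fails once the end date shows that the event was over before dosing, because nothing is then uncertain about its class. The SAP recognises this in the branch for a wholly missing onset but not in the two partial-date branches. A site that records the onset month can therefore get a worse classification than one that records nothing.

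At stake are the AE tables. Safety is the primary objective, AEs are its first-listed endpoint, and the study has 11 subjects, so one misplaced event can be visible in a percentage.

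**Working it through.** The plan gives no figure to reproduce. The check applies the rules literally to test records.

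**Inputs.** The onset and end-date rules are from SAP 6.7.3, and the TEAE boundaries from SAP 8.1 and 6.6.2. First dose is assumed at 22:00 on 20 September 2018: the date is illustrative, the hour is the 10pm dosing time in protocol 6.1.2. N = 11 is from SAP 4.3.

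**Rules as written.** The difference is imputed onset minus end, in calendar days; a positive value means onset after end.

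| Case | Recorded onset | Recorded end | Imputed onset | End used | Difference | TEAE, 8.1 | TEAE, 6.6.2 boundary |
|---|---|---|---|---|---|---|---|
| A | missing | 10 Sep | 1 Sep 00:00 | 10 Sep 23:59 | -9 | no | no |
| B | Sep 2018 | 10 Sep | 20 Sep 22:00 | 10 Sep 23:59 | +10 | yes | no |
| C | 2018 | 15 Aug | 20 Sep 22:00 | 15 Aug 23:59 | +36 | yes | no |
| D | 2018 | Aug 2018 | 20 Sep 22:00 | 31 Aug 23:59 | +20 | yes | no |
| E | 2018 | 19 Sep | 20 Sep 22:00 | 19 Sep 23:59 | +1 | yes | no |
| F | Sep 2018 | Sep 2018 | 20 Sep 22:00 | 30 Sep 23:59 | -10 | yes | no |
| G | Sep 2018 | 30 Sep | 20 Sep 22:00 | 30 Sep 23:59 | -10 | yes | no |
| H | Aug 2018 | 10 Sep | 1 Aug 00:00 | 10 Sep 23:59 | -40 | no | no |

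The difference for C is 16 days left in August plus 20 in September = 36.

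Cases B to E fail: the end is known, or imputed, to be before first dose, yet onset lands after it. A and B differ only in that B records the onset month, and B is the one that goes wrong. F and G are ambiguous and are handled conservatively. H is correct.

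**With the end-date check added.** If the end is before first dose, onset goes to day 1 of the end-date month. B becomes 1 September, C 1 August, D 1 August and E 1 September. All four then have onset before end and are not TEAEs. A, F, G and H do not change.

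**The boundary.** An imputed onset equals the first-dose date and time. SAP 8.1 includes it; the strict wording in 6.6.2 does not. Under the strict wording F and G are not TEAEs either, so no AE imputed to first dose would ever count, which defeats the purpose of imputing it there.

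**Size.** One subject in 11 is 1/11 = 0.0909, or 9.1 percentage points. A row rises by that amount only if the subject has no other event that already counts in it.

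**The case against.** The strongest reply is that the TEAE result is not certain. Under SAP 6.6.2 read strictly, an onset equal to first dose is not treatment-emergent, and both documents make the intended class of a pre-dose event plain. This stands as a limit on the consequence. It does not remove the onset-after-end result, which follows from 6.7.3 under either definition.

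A reader might also infer that such records are likely. The documents do not support that. The failure needs a pre-dose AE, a partial onset in the month or year of first dose, and an end known or imputed to fall before dosing; no rate of partial dates is given. The screening window is 12 weeks in the protocol but at most 30 days in the SAP schedule. The schedule's AE review row begins at baseline, yet protocol 8.2.4 has AEs assessed at every visit. Possible is as far as one can go.

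A reader might take 9.1 points as the expected bias. It is the effect of one affected subject, under the condition given above.

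Three further replies hold. No planned AE table summarises duration, so a negative duration would not reach a summary. SAP 8.1 lists all AEs by subject, so with 11 subjects an inverted record may be noticed. TEAEs are one part of a family of primary safety endpoints, and SAP 8 says that AE incidence is in general not tested.

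**Conclusion.** The point holds as a minor error in a stated rule. In both partial-date branches of SAP 6.7.3, an AE whose end is known or imputed to be before first dose receives an onset after that end. That it then enters the tables as a TEAE depends on applying SAP 8.1 or protocol 8.2.1 in preference to the strict boundary in SAP 6.6.2; on that basis the result contradicts protocol 8.2.4 and the SAP's own statement about pre-dose events.

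The direction is over-counting. The number of affected records is unknown and may be zero. The general practice of moving uncertain onsets to first dose is not at fault; only the missing end-date check is.

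**What to change.** In both partial-date branches of SAP 6.7.3 add an exception: if the AE end date, as recorded or imputed, is before first dose, apply the existing rule for a wholly missing onset (day 1 of the end-date month, 00:00) and classify the AE as non-treatment-emergent. Add a general requirement that imputed onset be no later than AE end.

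Use the end-month rule in preference to 1 January for year-only onsets. In case C, 1 January would date the event more than seven months before an August end and could place it well before consent. The end-month rule keeps one convention throughout the section and can precede the end date by no more than a month.

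Also settle the TEAE start boundary, so that SAP 6.6.2, Table 4 and 8.1 agree and ambiguous onsets imputed to first dose are counted as intended.

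The cost is one clause in each branch, one consistency check and one aligned definition. No new data are needed, and genuinely ambiguous onsets keep their conservative handling. If analysis has already begun, SAP section 2 provides for reporting a substantive change in the clinical study report.

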6.7.4. Missing Start and Stop Dates for Medications

To determine whether medications were used prior to initiation of dosing and whether they were used after initiation of dosing, missing or partial dates for medications will be imputed according to the following rule:

Missing medication start date/time:

- If only have a YEAR, impute as Jan. 1, at one minute after midnight.
- Else if only have YEAR and MONTH, impute as Day 1 of month, at one minute after midnight.
- Else if have a complete date, impute TIME as one minute after midnight.
- Else if completely missing, and ((end date is present and \geq date of first dose) or (end date is missing and is marked as “ONGOING”)), impute as date and time of first dose. If missing and end date/time is present and prior to date of first dose then leave as missing.

Missing medication end date/time:

- If only have a YEAR and it is same as year of study completion, impute as date of study completion with time of 23:59.
- Else if only have a YEAR, impute as December 31 with time of 23:59.
- Else if only have YEAR and MONTH, then impute to last day of the month, with time of 23:59.
- Else if have a complete date but no time, impute time of 23:59
- Else if end date/time completely missing and not flagged as Ongoing, impute as date of study completion with time of 23:59.

Otherwise missing, no imputation.

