## 1.2 Schema

### 1.3 Schedule of Activities

	Screening Period	Treatment Period								Follow-up/ET
		1  Screening	2 Baseline	3	4	5	6	7	8	
VISIT NUMBER		0	2	4	6	8	10	12	16	
STUDY WEEK										
STUDY DAY 	12 weeks before Day 1	1	15	29	43	57	71	85		Last dose +30 days
Site Visits 	X	X		X		X		X	X	
Home Visits 			X		X		X			
Informed consent	X									
Inclusion/exclusion criteria	X	X								
Demography 	X									
Medical history 	X									
Prior medications 	X									
Concomitant medications 	X	X	X	X	X	X	X	X	X	

 For subjects rolling over from Study SPR001-201, the final safety follow-up visit of Study SPR001-201 may coincide with the screening visit of this study (with any overlapping assessments conducted only once). If a subject completed the final follow-up visit of Study SPR001-201 ≤3 months before the screening period of this study, overlapping assessments conducted at that final follow-up visit need not be repeated at screening for this study. If a subject completed the final follow-up visit of Study SPR001-201 >3 months before the screening period of this study, all screening assessments must be conducted anew, including some additional screening assessments specified for such subjects.

 All visits should be performed on the indicated study days. In cases where this is not possible, the following visit windows apply: ±3 days for Visits 3 to 8 and ±7 days for the safety follow-up visit (Visit 9). All visits, including the early termination visit, should be scheduled for the morning, to accommodate 8am laboratory assessments.

 Study visits for screening; at Weeks 0, 4, 8, and 12; and at final follow-up must be conducted as in-clinic outpatient visits.

 Study visits at Weeks 2, 6, and 10 may be conducted as either in-clinic outpatient visits or in-home visits by qualified study personnel.

 Demographic information needs to be collected only for SPR001-naïve subjects.

 Full medical history and prior medications from the past year will be collected for SPR001-naïve subjects. If a subject completed the final follow-up visit in Study SPR001-201 before the screening period for this study, any significant medical history and medications taken during the intervening period should be captured.

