### 5.1 Eligibility Criteria for Subjects Who Completed Study SPR001-201

#### 5.1.1 Inclusion Criteria for Subjects Who Completed Study SPR001-201

Subjects who completed Study SPR001-201 must meet all of the following criteria to be eligible for this study:

1. Is approved by the Sponsor's Medical Monitor
2. Is on a stable regimen of glucocorticoid replacement for ≥12 weeks before baseline that is expected to remain stable throughout the study
3. If screening for this study occurs >3 months after the subject's final follow-up visit in Study SPR001-201, the subject will have serum 17-OHP measured at screening. On the day of screening, the subject should take any morning glucocorticoid medication after the screening blood draw to allow for an unimpeded assessment of 17-OHP. The subject will be included if screening shows 17-OHP ≥800 ng/dL.
4. Agrees to follow contraception guidelines ([Section 5.3.5](#)). Male subjects must also agree to refrain from donating sperm throughout the treatment period and for 90 days after the last dose of study drug.
5. Is able to understand all study procedures and risks involved and provides written informed consent indicating willingness to comply with all aspects of the protocol

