6.4.5. Examination of Subgroups

The following subgroups are pre-defined:

1. Sex: [a] male, [b] female
2. Baseline hormone control: [a] severe/moderate control issues, [b] mild control issues
3. Baseline Glucocorticoid category: [a] Non-Dexamethasone [b] Dexamethasone

Selected analysis will be conducted using the subgroup analysis sets.

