8.3. Concomitant and Other Medications

Concomitant medications, prescribed and over the counter, that the subject takes or continues to take after the baseline visit will be summarized according to the following rules.

Medications with a start date before the date of the first dose of study medication will also appear in the prior medication summary table. The same summary format applies here as it was described for the medication history and medications present at study entry tables with respect to major drug class, minor drug class, and generic name. The data will be presented by treatment group and for all treated subjects. The same subject counting procedures will also apply (e.g.,

major class frequencies will represent subjects only once even though the same subject can be counted for multiple minor sub-classes and generic names).

The supportive individual subject data listing should be organized as the medication history listings with trade and generic drug names, start and stop dates, days relative to the start of therapy, dose, frequency, route, and indication(s).

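### SAP 6.7.4 dates a medication with a completely missing start to the first dose, which takes background glucocorticoid out of the prior-therapy table although eligibility shows it was already in use

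*SAP*

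**What the plan says.** SAP 6.7.4 gives the purpose of its date rules: "To determine whether medications were used prior to initiation of dosing and whether they were used after initiation of dosing". It then works through the start date in order of how much is known.

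- Year only: "If only have a YEAR, impute as Jan. 1, at one minute after midnight". Year and month go to the first day of that month.
- Nothing known: the branch opening "Else if completely missing, and" applies if the end date is on or after first dose, or if the end date is missing and the record is flagged as ongoing. The instruction is then to "impute as date and time of first dose". If the drug ended before first dose, the start stays missing.

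SAP 8.3 states which drugs count as prior: "Medications with a start date before the date of the first dose of study medication will also appear in the prior medication summary table". SAP Table 4 opens the prior-medication window before first dose and closes it at first dose. SAP 7.7 plans a separate summary of glucocorticoids, indexed as Table 14.1.3.3 on the Safety set.

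On the background drug, Protocol 5.1.1 requires that a rollover subject "Is on a stable regimen of glucocorticoid replacement for ≥12 weeks before baseline that is expected to remain stable throughout the study". Protocol 5.2.1 requires the same of SPR001-naïve subjects, and 6.5.1 repeats it for everyone. The schedule in SAP 4.5 gives 30 days in place of 12 weeks.

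**The concern.** The rule exists to tell use before dosing from use after it. For the record with the least date information it chooses a start that rules out use before dosing. The partial-date branches lean the other way: they move the start to the beginning of the known period, which favours prior use.

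Setting an unknown onset to first dose is cautious for adverse events (SAP 6.7.3), because it makes the event treatment-emergent. For a medication the same device keeps the drug as concomitant but erases its use before dosing.

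The drug for which this is plainly wrong is glucocorticoid replacement. Every eligible subject was taking it before Day 1, so a background regimen imputed to first dose contradicts something the protocol guarantees. At stake is the accuracy of the prior-medication tables, and of Table 14.1.3.3 in particular, in a study of 11 subjects where one record is visible in a percentage.

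**Working it through.** The plan states no figure to reproduce. The check is to run record types through the 6.7.4 start rule and then through the 8.3 test (start date earlier than the date of first dose). For illustration, first dose is at 22:00 on 10 September 2018; 10pm is the dosing time in Protocol 6.1.2 and the date is arbitrary.

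| Start date recorded | End date or flag | Start after 6.7.4 | Prior under 8.3? |
|---|---|---|---|
| Completely missing | Ongoing | 10 Sep 2018, 22:00 | No |
| Completely missing | Ended after first dose | 10 Sep 2018, 22:00 | No |
| Completely missing | Ended before first dose | Left missing | No start to test; the end date itself shows pre-dose use |
| Completely missing | End missing, not flagged ongoing | No rule, unless the end date is imputed first | Undetermined |
| 2005 only | Ongoing | 1 Jan 2005, 00:01 | Yes |
| 2018 only (year of first dose) | Ongoing | 1 Jan 2018, 00:01 | Yes |
| Sep 2018 only (month of first dose) | Ongoing | 1 Sep 2018, 00:01 | Yes |

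The first two rows are the problem. They fail whether the comparison uses dates or dates with times, because the imputed start equals the first dose and is never earlier.

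Next, compare those rows with what is known. Under Protocol 5.1.1, 5.2.1 and 6.5.1 the true start of the stable regimen is at least 12 weeks before baseline; under SAP 4.5 it is at least 30 days before. Under either, a background glucocorticoid is prior, and the imputed answer is the opposite.

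Size, taking the final sample size of 11 from SAP 4.3 and assuming all 11 received a dose and so form the Safety set. With k affected subjects, a proportion in Table 14.1.3.3 moves by k/11:

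- k = 1: 1/11 = 9.1 points
- k = 2: 2/11 = 18.2 points
- k = 3: 3/11 = 27.3 points

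The documents do not give k, and it may be zero.

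**The case against.** The best case for leaving the rule alone has four parts.

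- **The branch may never be reached.** Protocol 6.5 requires start and end dates for every concomitant medication, and a lifelong drug will usually have at least a year, which 6.7.4 handles well. This stands. A reader might infer that chronic glucocorticoid is the drug most likely to lack a date, because the schedule of activities says "Full medical history and prior medications from the past year will be collected for SPR001-naïve subjects". That footnote limits which history is collected; it does not say that start dates are left blank.
- **Exclusion from the prior table is not stated outright.** SAP 8.3 says that earlier-starting drugs will also appear there, without saying that only those will. Table 4's stop at first dose could be read as inclusive. The heading of 7.7 also covers drugs present at entry, and the glucocorticoid logic in 11.2 has no date condition. This stands in part: exclusion is the likelier reading but not the only one. If the inclusive reading is meant, the SAP should say so.
- **The drug is not lost.** It stays in the concomitant table and listing. This stands.
- **A Day 1 steroid start changes no analysis.** A reader might infer that it would pass for a change in background therapy. The index in 11.3 contains no analysis of new steroid starts or glucocorticoid changes, and Protocol 6.5.1 has actual dosing changes recorded. This stands.

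None of this makes the imputed date right for a drug known to have been in use, and none of it gives a reason to keep the branch as written.

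**Conclusion.** The defect is real and minor. For a completely missing start on a drug that is ongoing, or that ended on or after first dose, SAP 6.7.4 read with 8.3 gives a result that conflicts with the rule's purpose and, for background glucocorticoid, with eligibility. It affects descriptive prior-medication tables by 9.1 points per affected subject. This rests on reading 8.3 as the test for the prior table, on a Safety set of 11, and on at least one such record existing.

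A reader might go further and infer that a dexamethasone subject could be misfiled as non-dexamethasone, which would disturb the 17-OHP, ACTH and androstenedione tables. The documents do not support that. SAP 6.4.5 only names the category ("Baseline Glucocorticoid category: [a] Non-Dexamethasone [b] Dexamethasone"), and 11.2 defines glucocorticoids by class text; neither derives the split from start dates. The outcome would depend on a derivation the SAP does not give. A test of start date on or before Day 1 classes the subject correctly; a test of start before first dose, or before the 8am pre-dose draw, does not. The regimen is also known separately, since the glucocorticoid assayed in the key-hormone samples depends on what the subject takes (Protocol 8.3.1). What is missing there is a definition, and no effect on a hormone result is shown.

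**What to change.** In SAP 6.7.4, replace the completely-missing branch with: a medication whose start date is completely missing, and which is ongoing or ended on or after first dose, is classified as both prior and concomitant, unless it was first recorded as new at a post-baseline visit.

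As a safeguard only, add to 6.4.5 that the baseline glucocorticoid category is taken from the regimen recorded at Day 1 and not from imputed dates.

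The cost is one sentence in each section, with no change to data collection. The downside is that a truly new drug with no start date, not identified as new at its visit, could also be listed as prior. It would still be counted as concomitant, so no on-treatment use is lost.
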